## 10) Risks to subjects

*Few risks or complications are posed to the study participants. Participation in either workshop involves interaction with other participants and possible discussion of personal background information that may be uncomfortable for some individuals. Some participants with sensitive skin may experience mild discomfort at the electrode sites for ECG data collection and around the wrist from wearing the Actiwatch. However, the equipment used for ECG recordings is widely used for research and clinical purposes with minimal adverse reactions reported, and the Actiwatch device has been tested for safety and has been FDA approved for use in adults.*

*Subjects will be instructed to report any skin irritations related to study procedures to research personnel and to seek medical care if the irritations persist longer than 24 hours.*

## 11) Potential benefits to subjects and/or society

*Benefit to participants is anticipated from both workshops in terms of stress-management tools and overall well-being, although some may benefit more than others in one workshop or the other. Participants may also benefit by contributing to scientific knowledge stress physiology and well-being in college students and other adults.*

## 12) Provisions to protect the privacy of subjects and the confidentiality of data

### a. Protection of subject privacy:

Participant contact will be conducted through a password-protected e-mail account designated specifically for the study. Information collected via online pre-screening survey will also involve password-protected access. The online nature of the screening survey allows for increased privacy of the participant, as individuals are able to complete the survey at the remote location of their choice without intrusions from study personnel or others from the laboratory. In-person informed consent will be conducted in a private room within the laboratory.

### b. Protection of data confidentiality:

Consent forms will be stored in a locked cabinet in Psychology 409 until the end of the study. Per Psychology Department guidelines, at the end of the study all consent forms will be moved to the Psychology main office, room 312. Each participant will be given a unique participant identifying number that will not be recorded on his or her consent form. This unique participant number only (and not any identifying information) will be recorded on all experimental data collected. Therefore, all of the data in Psychology 409 will be de-identified. The date of the participant's intake will be recorded on the consent form. This date will also be recorded in an excel sheet of de-identified participant data. Consent forms will be stored in the Psychology building for up to six years should data ever need to be re-identified, as requested by the IRB. De-identified data, including questionnaire information, will be secured indefinitely in electronic form on [name] secure server. Paper copies, with no identifying information, will be shredded once entered onto the server.

## 13) Subject compensation

The maximum total amount a participant may receive is \$100. Payment will be provided at two points across the study: \$60 upon completion of T2 and an additional \$40 upon completion of T3. This payment plan has been carefully devised to ensure adequate payment that is proportional to the challenge of maintaining commitment through the entire study, while not overly lucrative in order to minimize chance of possible coercion and/or substantial monetary motivation that would be detrimental to the workshop dynamics. To help ensure appropriate attendance at the workshops, which is critical to enable group cohesiveness as part of the workshop benefit for individual participants, payment will not be pro-rated for drop-outs prior to completion of T2.

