**b. Informed Consent:**

All interested individuals who are eligible for the study will undergo an in-person informed consent procedure prior to the first laboratory visit. Subjects, including workshop instructors, will be assigned identifying numbers and the association between the numbers and names will be destroyed upon completion of the study. No minors or individuals incompetent to provide informed consent will participate in the present study. They will be reminded that their participation in the study is entirely voluntarily, they may withdraw at any time, and they will be compensated for their time.

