**15) Withdrawal of subjects**

Participants may voluntarily withdraw at any time, as indicated in the consent form. Researchers may ask participants to cease participation in the study if study procedures are not followed (e.g. incomplete workshop attendance). In the event that a participant either undergoes adverse experiences associated with the workshop or voluntarily withdraws while the workshop is in progress, the workshop instructor will follow up with the participant to offer support, if needed, and help facilitate transition out of the study. In the event of withdrawal during laboratory visits, the researchers conducting the visit will likewise follow up with the participant to help facilitate transition out of the study. Withdrawal due to any adverse, study-related circumstances will be reported to the IRB.

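### Anyone who stops before T2 because of an adverse experience is paid nothing, which does not fit the protocol's own consent wording and gives a financial reason to continue

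*Protocol*

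**What the plan says.** All references are to Section 3 of the Protocol unless stated otherwise.

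- **Item 13, Subject compensation.** Payment comes in two parts, $60 on completing T2 and $40 on completing T3, with a maximum of $100. Before T2, "payment will not be pro-rated for drop-outs prior to completion of T2". The purpose given for this rule is "To help ensure appropriate attendance at the workshops", because group cohesion is regarded as part of the benefit. The same item says the payment plan was designed to keep the risk of coercion low.
- **Item 7b, Informed Consent.** Participants are reminded that taking part is voluntary, that "they may withdraw at any time, and they will be compensated for their time". No condition on payment is mentioned.
- **Item 15, Withdrawal of subjects.** The provision for exits during the workshop begins "In the event that a participant either undergoes adverse experiences associated with the workshop or voluntarily withdraws while the workshop is in progress"; the instructor then offers support and will "help facilitate transition out of the study". Researchers may also ask someone to stop if procedures are not followed, with missed workshop sessions as the example. The item ends: "Withdrawal due to any adverse, study-related circumstances will be reported to the IRB". It says nothing about payment.

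**The concern.** The protocol foresees that a workshop may cause an adverse experience and provides a supported way out. The payment rule, read as written, makes that way out worth $0 until T2 has been completed. The reason given for withholding payment is attendance, and that reason does not reach a person who stops because they have been harmed. For that person the rule also works against item 13's own aim of limiting coercion.

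Two things are at stake. The first is voluntariness: a distressed participant stands to lose the whole first payment by stopping, and item 7b has led them to expect payment for their time. The second is the record of harm. The event that the payment rule penalises is the same event on which the protocol's one stated report to the IRB depends.

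**Working it through.** **1. The plan's own figure.** $60 (T2) + $40 (T3) = $100, which matches the maximum in item 13.

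**2. Payment by time of stopping, for any reason, including harm.**

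| Participant stops | Paid | Forgone |
|---|---|---|
| Before completing T2 | $0 | $100 |
| After T2, before completing T3 | $60 | $40 |
| After T3 | $100 | $0 |

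The full loss is therefore confined to the period before T2 is complete. That period includes the T2 laboratory visit itself. Item 8 describes the three visits as identical, so T2 repeats the stress-induction task, and item 15 also foresees withdrawal during a laboratory visit.

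**3. Time given by then.** The recruitment text (item 7a) puts a laboratory visit at about 1 hour, and item 8 puts the YES+ workshop at 15 hours over four days. So 1 + 15 = about 16 hours by the end of Day 4, not counting questionnaires, sleep diary and actigraphy. Someone who stops earlier in the workshop has given less. The 15-hour figure is stated for YES+ only.

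**4. Items 7b and 13 side by side.** Take the YES+ participant who completes T1 and the whole workshop, is harmed, and does not complete T2. Item 7b has this person reminded of the right to withdraw and of compensation for time, without a condition. Item 13 pays this person nothing. No other section makes an exception or says whether the term drop-outs covers people who leave because of harm.

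**5. What is stated to reach the IRB.**

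| Event | Response stated | IRB report stated |
|---|---|---|
| Skin irritation (item 10) | Participant tells research staff; seeks care if it persists | No |
| Unexpected injury (item 14) | Session stopped; emergency services called | No |
| Adverse experience during the workshop, no withdrawal (item 15) | Instructor follow-up | No |
| Withdrawal for adverse, study-related reasons (item 15) | Follow-up | Yes |

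**6. Cost of an exception.** The most it can add is $60 per person. The documents give no expected number of adverse exits. If 5 to 15 of the 100 students are assumed, the ceiling is 5 × $60 = $300 to 15 × $60 = $900. Payments to 100 completers would be 100 × $100 = $10,000, against an award of $15,000 (Section 2, item 5). If those who leave are not replaced, total payments stay below $10,000, because each receives at most $60 in place of $100.

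**The case against.** The strongest reply is that item 13 is a reasoned choice. It weighs commitment, coercion and group cohesion, and caps the total at $100. It sets the specific terms, while item 7b only lists general reminders. On that view the wording of item 7b is incomplete, and a reader who infers a flat contradiction goes too far, since item 7b does not actually say that an early leaver is paid. This has some force. What stands is that the two items do not fit together for the participant in step 4, and that item 13's reasoning does not address people who stop because of harm.

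Several stronger readings are tempting, and the documents do not support them.

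- **That the consent form misleads participants.** It is a separate attachment (Section 4) and was not available. It may set out the payment terms in full.
- **That withdrawal is the only route by which harm is reported at all.** Item 10 has skin irritation reported to staff, and item 15 has an adverse experience followed up even without withdrawal. Only the narrower statement about the IRB holds.
- **That a participant must hide a reaction to be paid.** Payment depends on completing T2, not on silence or full attendance, and removal for missed sessions is discretionary. Someone could disclose a reaction, miss a day, complete T2 and receive $60. That route still requires going on to T2, so it does not help a person who needs to stop.
- **That the harms record will be biased downwards, mostly in YES+.** Neither document describes a harms endpoint or a harms analysis, and neither gives data on how the payment rule affects behaviour. Item 6 says certain psychiatric histories may be risk factors for adverse effects of the breathing, and excludes people who have them. It gives no rate for those enrolled.

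**Conclusion.** The point holds as a gap in the payment terms and a mismatch between sections. Following the plan as written, a person who stops because of an adverse experience before completing T2 receives $0, after up to about 16 hours in YES+. This gives a financial reason to continue at the moment when the protocol says leaving should be free and supported.

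The payment result and the mismatch rest on the text alone. The 16 hours rests on the approximate visit length and the YES+ workshop length. The effect on adverse withdrawals, and so on what reaches the IRB, is an inference. It is a fair one, because item 13 itself uses payment to influence attendance, but its size is unknown. The 5 to 15 exits are an assumption used only to price the remedy. No estimate, allocation or analysis in the SAP changes.

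**What to change.** - **Item 13:** keep the T2 rule for ordinary drop-outs. Add that anyone who withdraws, or is asked to stop, because of an adverse experience before completing T2 is paid for the parts completed, up to $60. State how the $60 is divided, for example across the T1 visit and the workshop days attended, since the protocol gives no split.
- **Item 7b:** state the payment terms, including the T2 condition and the exception, so that it agrees with item 13. Check the consent form and amend it if it does not already say this.

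The cost is a short amendment and at most $60 per affected participant. The downside is an occasional unfounded claim of an adverse reason, limited to the same $60. The incentive for ordinary attendance is otherwise unchanged.

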**14) Medical care and compensation for injury**

There is no expectation of risk for participants. No compensation will be available for medical care. If there should be an unexpected injury, the session will be terminated immediately and the researcher will contact emergency services.

**15) Withdrawal of subjects**

Participants may voluntarily withdraw at any time, as indicated in the consent form. Researchers may ask participants to cease participation in the study if study procedures are not followed (e.g. incomplete workshop attendance). In the event that a participant either undergoes adverse experiences associated with the workshop or voluntarily withdraws while the workshop is in progress, the workshop instructor will follow up with the participant to offer support, if needed, and help facilitate transition out of the study. In the event of withdrawal during laboratory visits, the researchers conducting the visit will likewise follow up with the participant to help facilitate transition out of the study. Withdrawal due to any adverse, study-related circumstances will be reported to the IRB.

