## 2) Purpose

Addressing the gap in the literature described above and to provide further preliminary data on the specific effects of YES+ on well-being and stress physiology, this study aims to evaluate measures of self-reported wellness across a variety of questionnaires, in addition to changes in heart rate variability and salivary cortisol levels with a stress induction task. To control for expectancy effects, overall time spent with the workshop, social contact, and exposure to cognitive stress management strategies that may influence the observed effects of YES+ not specific to the yogic breathing and deep social connectedness at the core of the YES+ targets, a comparison workshop with all of these potential supplementary contributors will be included, titled “Wisdom On Wellness” (WOW!).

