## 6) Study Population

**100 college students** (50% female) will be recruited into the current study. Persons expressing interest in the study will be screened along several health dimensions and invited to participate in the proposed research according to the following criteria:

- a) 18-35 years of age. This age range is recommended for the YES+ workshop to capture qualitative consistencies in the unique challenges that face college students and optimize social connectedness during the workshop.
- b) Current identification with student status, which may include undergraduate, graduate, continuing studies, or post-baccalaureate/pre-doctoral.
- c) No history of panic disorder, psychosis, or mania (with or without psychotic features), which may be risk factors for adverse effects of the yogic breathing intervention. These symptoms will be pre-screened via online questionnaire. The use of psychoactive medication will be monitored via sleep diary.
- d) No current substance dependence, assessed via online self-report pre-screening questionnaire.
- e) No current use of medications with known effects on sleep or stress physiology including antidepressants (SSRI, SNSI, NDRI, atypical, TCA, MAOI), antipsychotics, benzodiazepines, non-benzodiazepine receptor agonists, melatonin and melatonin receptor agonists, orexin/hypocretin receptor antagonists, barbiturates, mood stabilizers, anticonvulsants, anticholinergics, first generation antihistamines, and stimulants including NRI, antihypertensives, opioids, or systemic (non-topical) corticosteroids.

In addition, a total of **4 workshop instructors** are expected to enroll in this study to provide questionnaire information regarding expectancy of workshop benefit for participants. All instructors must have prior training with the specific workshop to be led.

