**8) Research procedures involved in the Human Research**

An overview of the study involvement is illustrated in Figure 1. Participation will include three laboratory visits at pre-workshop (T1), post-workshop (T2), and 1-2 month follow-up (T3) time points and four workshop sessions described below.

**Figure 1.** Overview of study timeline for each participant.

*Screening:* Interested participants will first be directed to an online pre-screening survey. The survey will begin with a prompt describing the study and requiring understanding via checkbox that the survey is for screening purposes. The survey will collect information such as name, e-mail address, date of birth, motivation for the study, student status, prior contemplative practice experience, ability to meet the time commitment, panic and bipolar symptoms, and potential affiliation with other

participants. If any of the exclusion criteria indicated above are met, the participant will be notified of ineligibility.

[figure not shown]
*Enrollment and randomization:* Eligible participants will be first grouped in clusters with any other participants with known affiliations stated in the online screener, in order to minimize possibility of learning about material of the other workshop, then assigned a workshop via random number generator.

*Laboratory Visits:* In-person laboratory visits will be conducted at the University of Arizona Respiratory Physiology Laboratory on the main UA campus. Workshops will be conducted in various buildings on the main UA campus depending on reservation availability.

Actigraphy, sleep diary, online questionnaires and practice logs measures will be completely remotely after the instruments are provided to participants during an in-laboratory visit.

In addition to actigraphy, sleep diary, online questionnaires, and home practice logs (for T2 and T3 time points) the following data will be collected during each laboratory visit: electrocardiography (ECG) with concurrent respiratory inductance plethysmography (RIP) and pulse oximetry recordings, as well as salivary cortisol at baseline, post-stress induction task, 30-min post-stress-induction-onset, and 45-min post. ECG, RIP belts, and pulse oximetry will be recorded continuously, in addition to the designated resting recording periods. An overview of the laboratory visit (identical across T1, T2 and T3) is provided in Figure 2.

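### Researchers may end study participation for incomplete workshop attendance after random assignment, with no visible provision for T2/T3 assessment and no stated analysis population: a risk of selection bias of unknown size and direction

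*Protocol*

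**What the plan says.** Protocol Section 3, 8) places random assignment at enrollment: eligible participants are grouped with known affiliates, "then assigned a workshop via random number generator". Screening asks about "ability to meet the time commitment". Laboratory visits follow at T1 (before the workshop), T2 (after it) and T3 (one to two months later). Section 8 also says: "Actigraphy, sleep diary, online questionnaires and practice logs measures will be completely remotely".

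Section 3, 15) then states: "Researchers may ask participants to cease participation in the study if study procedures are not followed (e.g. incomplete workshop attendance"). The power is discretionary and carries no attendance threshold. The rest of that section covers support, help in leaving the study, and reporting of adverse withdrawals to the IRB. It does not mention collecting outcomes afterwards.

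Section 3, 13) pays $60 on completion of T2 and $40 on completion of T3, and adds that "payment will not be pro-rated for drop-outs prior to completion of T2". Its reason for wanting attendance is group cohesion, "which is critical to enable group cohesiveness as part of the workshop benefit for individual participants".

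The SAP names linear mixed models, reports Visit, Group and Visit x Group, and puts its emphasis on within-group change from pre to post and from pre to follow-up, with Cohen's d. It does not say who is analysed, what happens to participants who were removed, or what is assumed about missing data.

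**The concern.** The rule lets study staff decide, after assignment, who goes on to supply outcomes. Someone removed before T2 contributes T1 data at most. If missing sessions is related to how much a person would have changed, the reported change describes those kept rather than those assigned. The SAP's focus on within-group change gives no protection, because no between-arm contrast is there to cancel the selection. Visit x Group is also reported, and the workshops differ in content: YES+ includes breathing practice and yoga, while WOW! is discussion without physical activity. Unequal attendance is therefore plausible, though not established.

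The stated reason for requiring attendance concerns how the workshop functions. It gives no reason to stop measuring outcomes.

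**Working it through.** The documents give no removal rate, effect size, SD or dropout allowance, so there is no plan figure to reproduce. What follows is an illustration.

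**Inputs from the documents**
- "100 college students" in total (Protocol Section 3, 6)).
- Four post-hoc comparisons per model, alpha 0.05 after Bonferroni (SAP), so 0.05/4 = 0.0125 each.

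**Assumptions**
- 50 per arm, as no allocation ratio is given.
- T1-T2 correlation 0.5. The variance of change is then 2 - 2 x 0.5 = 1, so one SD of change equals one SD of outcome.
- f = share of an arm removed. g = mean change in those retained minus those removed, taken as 0.3 to 0.8 SD.

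**Bias in within-group change when T1 data are kept**

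*Case 1: removal unrelated to T1 but related to change.* T1 carries no information about the loss, so bias = f x g.

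*Case 2: removal driven by change itself.* The covariance of T1 with change is 0.5 - 1 = -0.5, so the T1 gap is about -0.5g and the slope of change on T1 is -0.5. The model recovers 0.25g, leaving about 0.75 x f x g.

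*Case 3: removal dependent on T1 only.* Bias = 0.

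| f | g (SD) | Case 1 | Case 2 (0.75 x f x g) | Case 3 |
|---|---|---|---|---|
| 0.02 | 0.3 | 0.006 | 0.0045 | 0 |
| 0.05 | 0.8 | 0.040 | 0.030 | 0 |
| 0.10 | 0.3 | 0.030 | 0.0225 | 0 |
| 0.20 | 0.8 | 0.160 | 0.120 | 0 |

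A simulation of 2,000,000 participants agreed closely with these formulas; the largest difference was case 2 at f = 0.20, g = 0.8, which gave 0.123. All signs reverse if those removed would have gained more.

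**Scale**
- SE of a within-group change with independent participants: 1/sqrt(45) = 0.149 (10% removed) and 1/sqrt(40) = 0.158 (20% removed).
- Case 1: 0.03/0.149 = 0.20 to 0.16/0.158 = 1.01 SE. Case 2: 0.0225/0.149 = 0.15 to 0.123/0.158 = 0.78 SE.
- With assumed workshop groups of 10 to 25 and an intraclass correlation of 0.05, the design effects are 1 + 9 x 0.05 = 1.45 and 1 + 24 x 0.05 = 2.2. The SE at n = 40 becomes 0.190 and 0.235, and the top figure falls to 0.16/0.190 = 0.84 and 0.16/0.235 = 0.68 SE.
- With a true change of zero, case 1, independent participants and a two-sided 0.0125 test, the false-positive rate is about 0.014 at f = 0.05, g = 0.5 and 0.032 at f = 0.20, g = 0.5.

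**Visit x Group, case 1, g = 0.5 in both arms**
- Equal removal at 10%: 0.1 x 0.5 - 0.1 x 0.5 = 0.
- 20% of YES+ and 10% of WOW! removed: 0.2 x 0.5 - 0.1 x 0.5 = +0.05 SD. Reversed: -0.05 SD.

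**What continued assessment recovers, case 1**

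If a share r of those removed is assessed (taken as typical of those removed), bias = f x g x (1-f)(1-r)/(1-f+f x r).
- r = 0.5, f = 0.10, g = 0.3: 0.030 x 0.9 x 0.5/0.95 = 0.014.
- r = 0.5, f = 0.20, g = 0.8: 0.160 x 0.8 x 0.5/0.90 = 0.071.
- r = 1: 0.

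**The case against.** The best case for the plan has several parts.

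*Removals may be few.* The power is discretionary, screening asks about the time commitment, and payment waits until T2. Nothing in the documents supports 10-20% removed by researchers, and at 2-5% the bias is negligible. This stands, and it limits the size of the point.

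*Mixed models use all available observations.* They do, but with T1 alone they correct the loss only if removal is ignorable given T1. A reader might infer that the SAP restricts the analysis to completers. It does not; it is silent, and keeping partial data is consistent with its text.

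*Follow-up is not forbidden.* A reader might infer that removed participants cannot be assessed. The documents do not say so. The consent form, a separate attachment not available here, may also cover it, so the point is confined to the visible text.

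*Change among attenders is a legitimate target.* The study aims "to provide further preliminary data on the specific effects of YES+ on well-being and stress physiology", and within-group change is not a randomized comparison even when analysed as assigned. Both remarks stand. But the SAP does not adopt an attenders-only target, and a discretionary rule with no threshold would not define one.

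*Payment.* A reader might infer that a non-attender who completes T2 goes unpaid. Section 13 attaches the $60 to completing T2 and states no attendance condition; the clause on drop-outs concerns those who leave before then.

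**Conclusion.** The point holds as a risk and should be addressed. The plan contains a rule, not merely a gap, under which outcomes can be lost selectively after assignment, and the SAP does not say how that loss is handled.

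Size and direction are unknown. Within-group change is overstated if those removed would have gained less than the model predicts for them, unaffected if they would have gained as predicted, and understated if more. The range of about 0.02 to 0.16 SD at 10-20% removed rests on the assumed gap, the assumed correlation and removal being related to change. Its upper end, about 1 SE, needs 20% removed and a 0.8 SD gap together.

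Two stronger readings are not supported. The documents do not show that the reported changes will be inflated. Nor would an as-assigned statement in the SAP cure the problem: with T1 data only, all of the bias remains in case 1 and about 75% in case 2.

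**What to change.** **1. Protocol, if follow-up is still open (the main remedy).** Replace the sentence in Section 3, 15) with: *Participants who do not follow study procedures may be asked to leave the study. Incomplete workshop attendance alone may end workshop participation but not outcome assessment; T2 and T3 are still offered unless consent is withdrawn.* The attendance requirement itself stays with the investigators. Full visits are preferable, because questionnaires alone leave salivary cortisol and heart rate variability missing, and both are named aims. In Section 3, 13), only payment for questionnaires alone needs to be stated.

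**2. SAP, in any case.** Add: *All randomized participants are analysed in the workshop assigned, using all available data, including T1 data of those removed. Removals and withdrawals are reported by arm, time and reason. A sensitivity analysis varies the assumed change in participants without T2 or T3 data (for example, a delta adjustment).* This makes the bias visible and bounds it over the range examined.

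**Timing.** The attachments are dated July to September 2015, the expected length is 18 months and the SAP is dated 12/15/2017. A start in September 2015 would put the end near March 2017, so part 1 may be too late. No start or end date is given, so this is inference.

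**Cost.** T2/T3 visits and payments are already planned for all 100 participants. Keeping 2 to 20 non-attenders uses at most 2 x $100 = $200 to 20 x $100 = $2,000 of the 100 x $100 = $10,000 payment maximum, on a $15,000 award. It also uses 2 x 4 x 2 = 16 to 20 x 4 x 2 = 160 saliva samples and the visits, each run by two researchers. The incentive to attend may weaken, by an amount the documents do not allow to be estimated.

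### The risk section omits the breathing practice and the ice-water stress task, no question on unwanted effects of the workshop or home practice is described, and the SAP has no harms summary

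*Protocol*

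**What the plan says.** **Risks.** Protocol Section 3, 10) opens with "Few risks or complications are posed to the study participants". It then lists uncomfortable personal discussion in either workshop and skin or wrist discomfort from the ECG electrodes and Actiwatch. Its one reporting instruction is "Subjects will be instructed to report any skin irritations related to study procedures to research personnel". Section 14) states "There is no expectation of risk for participants" and adds: "If there should be an unexpected injury, the session will be terminated immediately and the researcher will contact emergency services".

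**Exposures.** Section 6) c) excludes a history of panic disorder, psychosis or mania, "which may be risk factors for adverse effects of the yogic breathing intervention". Section 8) has YES+ participants practise SKY daily at home after the workshop. At all three laboratory visits it uses a stress task with hand immersion in water at about 2 °C for up to 90 seconds, alternating with mental arithmetic under neutral or negative feedback. Participants may take the hand out whenever they wish.

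**Follow-up and reporting.** Section 15) covers a participant who "undergoes adverse experiences associated with the workshop" or who withdraws during the workshop; in either case "the workshop instructor will follow up with the participant to offer support, if needed". The IRB rule is: "Withdrawal due to any adverse, study-related circumstances will be reported to the IRB".

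**Measurement and analysis.** Section 8) collects visual analog scale (VAS) ratings from 0 to 100, including discomfort or pain and distress, throughout each laboratory visit. It presents them as momentary stress ratings. The SAP describes linear mixed models and within-group comparisons. It does not mention harms.

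**The concern.** The two most demanding exposures in the study are missing from the section meant to list its risks, and another section says that no risk is expected. The reporting rule as written depends on withdrawal. A participant who has a bad reaction to the breathing but stays would be offered support, yet the text calls for no record or report of it.

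Withdrawal may also be an insensitive marker of harm here. Under Section 13), the first $60 of the $100 is paid on completing T2 and is not pro-rated for those who leave earlier, so someone who leaves before T2 receives nothing.

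The trial will compare two workshops on benefit. Without a described question on unwanted effects or a planned count, a statement on harm by arm would rest on spontaneous reports with no known denominator.

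**Working it through.** The plan gives no figure on this point, so the main check sets the sections side by side. The arithmetic only shows what asking participants would make possible.

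**1. Exposures against the risk section**

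| Exposure | Where described | In Section 10)? |
|---|---|---|
| Group discussion and disclosure | Section 8), both workshops | Yes |
| ECG electrodes, Actiwatch | Section 8), Measures | Yes |
| SKY breathing, including daily home practice | Sections 6) c) and 8) | No |
| Ice water and negative feedback | Section 8), Stress Induction | No |

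Section 14) expects no risk, Section 10) a few, Section 6) c) possible adverse effects of the breathing in some people, and Section 15) provides for adverse workshop experiences.

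**2. How an unwanted effect could become a record**

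| Route | What it covers | What the text says follows |
|---|---|---|
| Adverse withdrawal, 15) | Those who leave | IRB report |
| Adverse workshop experience, 15) | Those who stay or leave | Instructor support; no log described |
| Injury, 14) | Sessions | Session stopped, emergency services; no report described |
| Skin irritation, 10) | Spontaneous self-report | Told to staff; medical care if it lasts beyond 24 hours |
| VAS, 8) | All participants at laboratory visits | Scored as a stress rating |
| Practice log, 8) | Use of techniques | Unwanted effects not mentioned |
| Day 1 and Day 4 forms, 8) | Expectancy and credibility, given as examples | Unwanted effects not mentioned |

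The VAS puts questions on discomfort and distress to every participant with a known denominator, but only around the laboratory task. Nothing described does the same for the workshop or home practice.

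**3. What a count could show.** Section 6) plans 100 students. The allocation ratio is not stated, so 50 per arm is an assumption; 35 is an assumed lower number asked. Clustering is ignored. For 0 events among n asked, the exact two-sided 95% upper limit is 1 − 0.025^(1/n):

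- n = 50: 1 − 0.025^(1/50) = 7.1%
- n = 35: 1 − 0.025^(1/35) = 10.0%

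The chance of at least one event among 50 asked is 1 − (1 − p)^50. For assumed true rates of 1%, 2%, 5% and 10% it is 39.5%, 63.6%, 92.3% and 99.5%. If nobody is asked, zero reports support no such limit.

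**4. Could the planned scales replace a question?** One option is to count participants who worsen from T1 by at least 1 baseline SD. With no true change, equal SDs, normality and T1–T2 correlation r, the SD of change is √(2(1 − r)) baseline SDs:

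- r = 0.5: SD of change 1.00, P(Z > 1.00) = 15.9%
- r = 0.8: SD of change 0.632, P(Z > 1.58) = 5.7%

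The correlations are assumptions. Some 6% to 16% would cross by noise on each scale at each visit. State STAI is completed at the stress-task visit with no stated timing relative to the task, so a rise may be the intended stress response.

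**5. Timing.** The latest attachment is dated 09/16/2015 and the SAP 12/15/2017, about 27 months apart, against an expected project length of 18 months. Data collection may be over, but the documents do not say so.

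**The case against.** The strongest reply has four parts.

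- **Safeguards and measurement exist.** Psychiatric histories are screened out, the hand may be withdrawn, sessions stop after an injury and instructors follow up. ECG, respiration and pulse oximetry run continuously at laboratory visits, and discomfort and distress are rated there. This stands, and it rules out one tempting inference, that nobody is ever asked about discomfort. The gap left is the workshop and home breathing.
- **The sections do not strictly conflict.** Section 6) c) concerns people who are excluded, Section 15) is conditional, and Section 14) deals with injury care. This has some force. Still, Section 10) concedes a few risks where Section 14) expects none, and a sentence giving adverse effects of the breathing as a reason for exclusion shows that the authors had such effects in mind. Screening is by online self-report.
- **Silence is not a rule.** A reader might infer that adverse experiences in those who stay are never reportable. The documents do not support that. Section 15) says what happens on withdrawal; institutional rules are not in the documents and may require more.
- **The forms were not available.** The consent form, debrief, questionnaire packets, Day 1 and Day 4 forms and practice log are listed in Section 4 as separate documents. None of the 19 titles refers to adverse events or monitoring, but titles do not show content. It cannot be inferred that participants were not told of these risks or not asked about effects.

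None of this supplies a harms summary in the SAP or puts the two missing exposures into Section 10).

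**Conclusion.** The point holds in limited form. On the text, Section 10) omits the SKY breathing and the stress task, and Section 14) fits poorly with Sections 6), 10) and 15). The only IRB report described is for adverse withdrawal. No question on unwanted effects of the workshop or home practice is described, and the SAP has no harms summary.

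The size of any harm cannot be estimated, because the documents give no event rate. The 7.1% and 10.0% limits rest on assumed numbers asked and independent participants; they show what a count could bound, not how large the defect is. Efficacy inference is unaffected. A reader might go further and conclude that the trial was unsafe or that harms were concealed; nothing in the documents supports either.

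This should be put right as a cheap improvement. Confidence is medium, because unseen attachments and institutional rules may close part of the gap.

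**What to change.** **Whether or not collection is complete,** add one SAP line reporting by arm: adverse withdrawals, injuries and recorded adverse experiences, with the number of participants asked; and VAS discomfort or pain and distress by visit. If no form asked about unwanted effects, state that harms were not systematically collected. The table is descriptive. A count of 1-SD worsening should be dropped, or kept only as an optional descriptive item without state STAI and compared between arms.

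**If participants are still in the study,** also:

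- reword Section 15) so that adverse, study-related experiences are logged, and reported as IRB rules require, whether or not the participant withdraws;
- add the breathing practice and the stress task to Section 10), correct Section 14), and check that the consent form agrees;
- add one identically worded question on unwanted effects to the Day 1 and Day 4 participant forms and the T2 and T3 packets in both arms, unless they already contain one.

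**Cost.** With collection complete: one SAP line and one table. With participants still in the study: also one IRB amendment and slightly longer forms. No efficacy analysis changes.
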